#### 7.1.3.2 Safety and PD Biomarker Data

Depending on the statistical analysis method, a single value may be required for each analysis visit window (e.g., CFB by visit usually requires a single value), except for ">90 Days Post Last Dose" analysis visit window.

For safety data, if multiple valid, non-missing, continuous records exist in a post-baseline analysis visit window, records will be chosen based on the following rules if a single value is needed, unless otherwise specified:

- The record closest to the target day (in terms of days) for that visit will be selected.
- If there are multiple records that are equidistant from the target day (in terms of days), the later record will be selected.
- If there are multiple records on the same day (regardless of time), the average value will be taken.

For exploratory PD biomarker data, if multiple valid, non-missing, continuous records exist in a post-baseline analysis visit window, then the average value of these records will be taken.

For safety and exploratory PD biomarker data, if multiple valid, non-missing, categorical records exist in a post-baseline analysis visit window (not applicable to categorical measurements derived from continuous measurements), records will be chosen based on the following rules if a single value is needed, unless otherwise specified:

- The record closest to the target day for that visit (in terms of days) will be selected.
- If there are multiple records that are equidistant from the target day (in terms of days), the later record will be selected.
- If there are multiple records on the same day, the record with the worst severity will be selected, for example:
  - o higher grade severity will be selected over lower grade severity for toxicity grades;

Protocol No. AL002-2 Last Revision Date: 12 Aug 2025

- o "low" or "high" will be selected over "normal" for a test or exam with those categories;
- o "abnormal" will be selected over "normal" for a test or exam with those two categories;
- o "positive" will be selected over "negative" for a test or exam with those two categories.

For those categorical measurements derived from continuous measurements, if multiple valid, non-missing, continuous records exist in an analysis visit window, the rules for selecting a single value for continuous measurements apply first, then the corresponding categorical measurements will be derived based on the single selected continuous measurements.

Measurements that are collected both predose and post-infusion also follow the above rules for post-baseline visits, but per each measurement time point (i.e., per predose, per post-infusion, and not applicable).

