7.11.1.2. Participant Follow-up for ARIA Events

Participants with new or worsening radiographic evidence of ARIA on post-baseline MRI scans should be evaluated for neurological signs or symptoms during an unscheduled visit.

Investigators should comprehensively review the BMW for the presence of ARIA or other abnormalities. When ARIA has been detected, follow-up BMWs should be reviewed for radiographic evolution/resolution/stabilization of findings. Investigators suspecting ARIA that has not been detected by the MRI Central Reader should contact the Medical Monitor. For instance, if a local radiologist detects a faint area of vasogenic edema or microhemorrhage, which was not documented in the BMW, the Investigator should contact the Medical Monitor.

Alector, Inc.

If participants are determined to have ARIA-related symptoms or signs, the Medical Monitor should be contacted within 48 hours. Investigators should be aware of the symptoms most commonly observed in participants with symptomatic ARIA. ARIA-related symptoms are typically non-localizing such as headache, confusion, visual changes, dizziness, nausea, and gait difficulty. However, in some cases, focal neurological deficits (eg, visuospatial difficulty, aphasia, and apraxia) may occur. Serious ARIA symptoms can include encephalopathy, stupor, seizures, and status epilepticus (Cummings 2023, Cogswell 2022).

Participants with asymptomatic ARIA-E may be observed; for participants with mild or moderate symptomatic ARIA-E, the use of oral or IV steroids may be considered (see Table 7). In the case of severe symptomatic ARIA-E, it is recommended to hospitalize the participant for close observation and consider the use of IV steroids such as high-dose dexamethasone or a similar agent.

All new cases of ARIA-E and/or new cases of ARIA-H will require unscheduled MRI scans every 4-6 weeks until ARIA-E has resolved and/or until ARIA-H has stabilized without new findings. In addition, the Sponsor may request that additional unscheduled MRIs be performed for the detection and follow-up of ARIA.

An Amyloid PET scan should be requested after the first occurrence of ARIA-E and/or ARIA-H for those participants who have opted-in to have longitudinal Amyloid PET performed. An unscheduled LP for CSF analysis and plasma may be requested, if not contraindicated, after any occurrence of ARIA-E and/or ARIA-H.

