## 7.1.1.2.3 Fluid (Plasma, CSF) and PET Imaging (Amyloid and Tau) Biomarker Data

Analysis visit windows for the biomarker parameters are defined in a similar manner as those for the efficacy parameters. Biomarker data will be allocated to analysis visits corresponding to the analysis visit window intervals in which they fall in as specified in Table 7-15 to Table 7-19.

Table 7-15. Analysis Visit Windows for PD Plasma Biomarker Assessments

Analysis Visit	Target Day	Analysis Visit Window (Based on Study Day)
Baseline	1	≤ 1
Week 1	8	[2, 12]
Week 2	15	[13, 22]
Week 4	29	[23, 36]
Week 6	43	[37, 50]
Week 8	57	[51, 71]
Week 12	85	[72, 99]
Week 16	113	[100, 141]
Week 24	169	[142, 211]
Week 36	253	[212, 295]
Week 48	337	[296, 379]
Week 60	421	[380, 463]
Week 72	505	[464, 547]
Week 84	589	[548, 631]
Week 96	673	≥ 632

Table 7-16. Analysis Visit Windows for CSF Biomarker Assessments

Analysis Visit	Target Day	Analysis Visit Window (Based on Study Day)
Baseline	1	≤ 1
Week 6	43	[2, 190]
Week 48	337	[191, 421]
Week 72	505	[422, 589]
Week 96	673	≥ 590

Protocol No. AL002-2 Last Revision Date: 12 Aug 2025

Table 7-17. Analysis Visit Windows for Amyloid PET Assessments

Analysis Visit	Target Day	Analysis Visit Window (Based on Study Day)
Baseline	1	≤ 1
Week 48	337	[2, 505]
Week 96	673	≥ 506

Table 7-18. Analysis Visit Windows for Tau PET Assessments, True Baseline\*

Analysis Visit	Target Day	Analysis Visit Window (Based on Study Day)
Baseline	1	≤ 1
Week 48	337	[2, 421]
Week 72	505	[422, 589]
Week 96	673	≥ 590

\*True baseline: baseline corresponds to the pre-dose visit (prior to dosing).

Table 7-19. Analysis Visit Windows for Tau PET Assessments, Redefined Baseline (Sensitivity Analysis)\*

Analysis Visit	Target Day	Analysis Visit Window (Based on Study Day)
Baseline_R	1	≤ Day 1 Predose, if it exists. If not, then day of Week_R 48 nonmissing result (up to Day 421)
Week_R 48	337	[2, 421]
Week_R 72	505	[422, 589]
Week_R 96	673	≥ 590

\*Redefined baseline: baseline corresponds to either the pre-dose visit (prior to dosing) if the pre-dose Tau PET scan is evaluable, or 1st postdose visit if the pre-dose Tau PET scan is missing.

Protocol No. AL002-2 Last Revision Date: 12 Aug 2025

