For amyloid PET centiloids measure, the number of participants with amyloid clearance (positive [centiloids ≥ 24.1] at baseline and negative [centiloids < 24.1] at week 48), and percentage with 95% CI (mid-p method), will be summarized by treatment group. Treatment comparison (vs. placebo) will be based on mid-p method.

Additional analyses based on supportive estimand will be provided for Tau PET ROIs [subset 1] for the subset with redefined baseline (descriptive summary, MMRM and pMMRM), and amyloid PET ROIs (descriptive summary and MMRM) [Table 7-25].

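### ARIA-triggered amyloid PET scans and lumbar punctures are averaged into, or stand in for, the Week 48 amyloid and Week 6 CSF values

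*SAP*

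**What the plan says.** **Triggered assessments.** Protocol 7.11.1.2 states: "An Amyloid PET scan should be requested after the first occurrence of ARIA-E and/or ARIA-H for those participants who have opted-in" to longitudinal amyloid PET. The synopsis and Protocol 6.5.12 word this as an option, not a recommendation. For CSF, 7.11.1.2 adds: "An unscheduled LP for CSF analysis and plasma may be requested, if not contraindicated, after any occurrence of ARIA-E and/or ARIA-H".

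**Allocation to visits.** SAP 7.1.1.2.3 uses study day alone: "Biomarker data will be allocated to analysis visits corresponding to the analysis visit window intervals in which they fall in". Table 7-17 gives amyloid PET a Week 48 window of Days 2–505 (target Day 337). Table 7-16 gives CSF a Week 6 window of Days 2–190 (target Day 43).

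**Several records in one window.** For biomarkers, SAP 7.1.3.2 says: "For exploratory PD biomarker data, if multiple valid, non-missing, continuous records exist in a post-baseline analysis visit window, then the average value of these records" is used. For continuous safety data, the same section says: "The record closest to the target day (in terms of days) for that visit will be selected". SAP 7.1.3.1 uses that closest-record rule for efficacy too.

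**Use of the values.** SAP 7.7.1.1 models amyloid PET at Week 48 and CSF at Weeks 6, 48 and 72. It also counts "the number of participants with amyloid clearance (positive [centiloids ≥ 24.1] at baseline and negative [centiloids < 24.1] at week 48". SAP 7.7.2 relates Week 48 amyloid change to Week 48 CDR-SB change.

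**The concern.** A scan or lumbar puncture done because ARIA was found is timed by the event, not by the visit schedule. The windows are wide enough to take in nearly all such records, and the averaging rule gives them the same weight as the scheduled record. If there is no scheduled record in the window, the triggered one becomes the visit value.

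At stake are the Week 48 amyloid change, the clearance count, the amyloid–CDR-SB association and the Week 6 CSF comparison. Protocol 1.3 lists ARIA as an identified risk of AL002, so the share of mistimed values may differ between arms. That would matter most for a comparison with placebo.

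**Working it through.** **1. Reproduce the windows.** The upper bounds are midpoints of adjacent target days.
- Amyloid PET Week 48: (337 + 673)/2 = 505.
- CSF Weeks 6, 48 and 72: (43 + 337)/2 = 190; (337 + 505)/2 = 421; (505 + 673)/2 = 589.

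All agree with the SAP. The lower bound of the first window is simply Day 2.

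**2. Widths.**
- Amyloid PET Week 48: 505 − 2 + 1 = 504 days, opening 335 days before target.
- CSF Week 6: 190 − 2 + 1 = 189 days, running 147 days past target.
- For comparison: efficacy Week 48 is 168 days (254–421), plasma Week 48 is 84 days (296–379) and plasma Week 6 is 14 days (37–50).

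**3. When triggered records can arise.** Part 2 surveillance MRIs fall 5–10 days before Day 29, Day 57 and Week 13, then before Weeks 25, 49, 73 and 97 (Protocol 7.11.1.1). The first is at about Day 19–24. Any amyloid PET that follows, up to Day 505, is coded Week 48.

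**4. Does another rule remove them?** The main PD estimand follows the primary estimand (SAP Table 2-1). SAP 6.2.1.2 drops data only from 37 days after premature discontinuation. Protocol Table 7 suspends dosing for most ARIA findings and does not end it, so the cut-off seldom applies. Where treatment does end, a triggered scan within 37 days is kept while the Week 49 scan may be dropped, which leaves the triggered scan alone. The supportive estimand, also applied to amyloid PET, has no such cut-off.

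**5. Averaged or alone.**
- PET: averaged with the Week 49 scan if there is one, otherwise alone as Week 48.
- CSF, Part 1: averaged with the Day 43 sample.
- CSF, Part 2: Protocol Table 9 schedules no lumbar puncture in Days 2–190, so a triggered sample stands alone as Week 6 and is pooled with Part 1 Day 43 samples.
- A triggered CSF sample on Days 191–421 goes into Week 48 CSF.
- Under the Table 9 footnotes, PET within 24 weeks or CSF within 12 weeks is not repeated at the efficacy follow-up or early termination visit. A triggered record can therefore displace a later one.

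**6. Illustration for PET.** *Assumption: change is linear from Day 1; the documents give no trajectory.* A scan on day d shows (d − 1)/336 of the Day 337 change. Averaged with Day 337, the pair shows ((d + 337)/2 − 1)/336.

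| Triggered scan | Alone | Averaged with Day 337 |
|---|---|---|
| Day 24 | 23/336 = 7% | 179.5/336 = 53% |
| Day 80 | 79/336 = 24% | 207.5/336 = 62% |
| Day 160 | 159/336 = 47% | 247.5/336 = 74% |

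If a share q of an arm has such a scan and the individual fraction is f, the arm mean keeps 1 − q(1 − f). For Day 80, with q running from 5% to 30% (assumed; nothing in the documents supports a value), the arm mean keeps 98% to 89% when averaged and 96% to 77% when alone.

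**7. Illustration for clearance.** SAP 7.1.3.2 derives categories after the single continuous value has been formed. *Assume 80 centiloids at baseline and 10 at Day 337, linear.* The Day 80 value is 80 − 70 × 79/336 = 63.5, and the average is (63.5 + 10)/2 = 36.8. That is above 24.1, so this participant counts as not cleared although the scheduled scan is negative.

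**8. Association analysis.** The CDR-SB value for Week 48 is the record closest to Day 337 within Days 254–421. The amyloid value paired with it may be an average reaching back to the first weeks, so the timepoints match in label only.

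**The case against.** The strongest reply is that few records are likely to be involved and that nothing confirmatory depends on them. The PET request covers only opted-in participants at a first ARIA, and radiation limits apply. The lumbar puncture is optional. PD analyses use the FAS, which excludes e4/e4 participants, the genotype in which serious and severe symptomatic ARIA occurred (Protocol 1.3). Placebo participants with ARIA are handled the same way. The PD endpoints are exploratory, with no multiplicity adjustment. All of this stands and limits the likely size. None of it removes a triggered record from the analysis.

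A reader might go further in several ways that the documents do not support:
- *That the rule shrinks the amyloid effect in participants with the strongest vascular amyloid reaction.* Protocol 7.11 leaves open whether these MRI findings relate to amyloid at all, and no amyloid trajectory is given.
- *That a definite fraction of the active arms is affected.* No ARIA rate by arm is stated.
- *That triggered CSF values are too early.* Most of the Week 6 window lies after Day 43, so they will often be late.
- *That Part 1 supplies at most ten CSF samples per arm, so two or three triggered ones would dominate.* Protocol 3.1.3 makes ten a minimum per dose level, and 3.1.10 allows Part 1 to grow. Exclusions and dropout may lower the analysed number, but the documents do not give it.

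**Conclusion.** The point holds as a fault in a stated rule. Followed as written, the SAP assigns event-timed amyloid PET and CSF values to Week 48 and Week 6, by averaging or by substitution, and the clearance count and the CDR-SB association inherit them.

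For one participant the distortion can be large: about 62% of the Day 337 change retained when a Day 80 scan is averaged in, and about 24% when it stands alone, if change is linear. The effect on an arm or a treatment comparison cannot be sized or signed, because ARIA rates by arm, uptake of the optional scans and the amyloid trajectory are not given. A difference between arms is plausible, given that ARIA is an identified risk, but it is not shown.

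The damage is confined to exploratory endpoints. The CDR-SB analyses use the closest-record rule and are not affected.

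**What to change.** In SAP 7.1.3.2, for PET and CSF biomarkers:
1. Select the record closest to the target day, and average only same-day replicates.
2. Flag records collected as ARIA follow-up. In the main analysis, leave them out of the visit-based models and the clearance count, and list or summarise them separately. Closest-record selection alone is not enough, because it does nothing for a triggered record that is the only one in its window.
3. Add a sensitivity analysis that includes the flagged records, because excluding a participant's only record creates missing data linked to the event.

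If the windows are also narrowed, raise the lower bound of amyloid PET Week 48 (for example to Day 254, as for efficacy) and keep the upper bound at Day 505. Stopping at Day 421 would leave Days 422–505 unassigned, since Week 96 starts at Day 506. Limit CSF Week 6 to days around Day 43; the SAP's plasma Week 6 window of Days 37–50 is one model. Records before these bounds would then deliberately belong to no visit.

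The plasma rule can stay, with ARIA-triggered samples flagged.

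The cost is SAP wording, one programming flag and one extra sensitivity analysis. A few early values leave the models but remain in the listings.

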#### 7.1.4 Data Handling Conventions and Transformations

#### 7.1.4.1 Conversion of Categorical Values to Numerical Values

For non-PK data that are continuous in nature, certain categorical values will be converted to numerical values for calculating summary statistics. For non-PK data that are categorical in nature (i.e., all possible outcomes are categorical), no conversion from categorical values to numerical values will apply for calculating summary statistics, unless otherwise specified.

## 7.1.4.1.1 Handling of LLOQ and ULOQ

Non-PK data that are continuous in nature (e.g., safety lab tests) but are less than the LLOQ or above the ULOQ will be imputed as follows:

- A value that is 1 unit less than the LLOQ will be used to calculate descriptive statistics if the datum is reported in the form of "< x" (where x is considered the LLOQ). For example, if the values are reported as < 50 and < 5.0, values of 49 and 4.9, respectively, will be used to calculate summary statistics. An exception to this rule is any value reported as < 1 or < 0.1. For values reported as < 1 or < 0.1, a value of 0.9 or 0.09, respectively, will be used for calculating summary statistics.
- A value that is 1 unit above the ULOQ will be used to calculate descriptive statistics if the datum is reported in the form of "> x" (where x is considered the ULOQ). Values with decimal points will follow the same logic as above.
- The LLOQ or ULOQ will be used to calculate descriptive statistics if the data is reported in the form of " $\leq$  x" or " $\geq$  x" (where x is considered the LLOQ or ULOQ).
- "Occasional" will be assigned 1 unit less than the LLOQ. An exception to this rule is if LLOQ is 1 or 0.1, a value of 0.9 or 0.09, respectively, will be used for calculating summary statistics.

## 7.1.4.1.2 Handling of Other Special Characters

Non-PK data that are continuous in nature but have a "x - y" interval value will be imputed as best of "x - y" for baseline and worst of "x - y" for post-baseline as their continuous numeric value, if needed for calculating summary statistics.

Non-PK data that are continuous in nature but have "None" representing zero will be assigned 0, if needed for calculating summary statistics.

Protocol No. AL002-2 Last Revision Date: 12 Aug 2025

Non-PK data that are continuous in nature but have "ND (not done)", "QNS (quantity not sufficient)", "NR (no result(s))", or "Non-evaluable" representing non-valuable or missing value will be assigned missing, if needed for calculating summary statistics.

#### 7.1.4.1.3 Handling of Special Laboratory Categorical Data

For a laboratory test that is continuous in nature but only had numeric values present when the result was abnormal but absent when the result was normal (e.g., when urine protein was normal (i.e., negative or absent), no numeric value was present in data), the numeric value will be assigned 0 corresponding to a normal (negative or absent) test result, and it is not considered as missing or unknown.

## 7.1.4.2 Handling of Predose and Post-infusion

For vital signs and ECG data that collect measurement time points (predose, post-infusion, or "Not Applicable") on a study drug administration day, the following rules apply for assigning the measurement time points, when applicable.

- (1) For the assessments collected on Study Day 1:
  - The entries on the corresponding electronic CRF (predose, post-infusion) will be used.
    - o If the entry on the corresponding electronic CRF is "post-infusion", the assessment will be assigned the analysis visit "Day 1 Postdose". Measurement time points are not applicable for "Day 1 Postdose".
    - o If the entry on the corresponding electronic CRF is "predose", it will be considered as a candidate for baseline, and the baseline selection rules apply. Measurement time points are not applicable for baseline.
- (2) For the assessments collected at a post-Study-Day-1 scheduled visit, in which study drug is administered per the Schedules of Assessments in the protocol, the entries on the corresponding electronic CRF (predose, post-infusion) will be used, if the date of assessment is prior to or on the last dose date.
- (3) For the post-Study-Day-1 visits in which study drug is not administered per the Schedules of Assessments in the protocol, including Week 3 (vital signs only), Unscheduled, EFU, SFU, and ET, "Not Applicable" will be assigned as the measurement time point.
- (4) For the assessments collected after the last dose date, "Not Applicable" will be assigned as the measurement time point. And this takes precedence over the entries on the corresponding electronic CRF.
- (5) For the assessments collected prior to the first dose date, the measurement time points do not apply. And this takes precedence over the entries on the corresponding electronic CRF.

## 7.1.4.3 Handling of Baseline being Zero

For an endpoint, the percent change from baseline (PCFB) at a post-baseline visit is calculated as follows:

((post-baseline value – baseline value) / baseline value) × 100%

If the baseline is 0 and the post-baseline value is also 0, then the PCFB is set to 0. If the baseline is 0 and the post-baseline value is non-zero, then the PCFB is set to missing.

Protocol No. AL002-2 Last Revision Date: 12 Aug 2025

## 7.2 Participant Disposition and Protocol Deviations

#### 7.2.1 Participant Enrollment and Disposition

The number of participants screened, the number (percent) of participants who failed screening, and the reasons for screen failure will be summarized. A summary of participant enrollment will be provided by treatment group, AL002 40 and 60 mg/kg combined group, total AL002 group, and overall for each country, as well as for each investigator within a country. The summary will present the number and percentage of participants enrolled. For each column, the denominator for the percentage calculation will be the total number of participants analyzed for that column.

The randomization schedule used for the study will be listed.

A summary of participant disposition will be provided by treatment group, AL002 40 and 60 mg/kg combined group, total AL002 group, and overall. This summary will group participants according to the assigned treatment for all analysis sets. This summary will present the number of participants screened, the number of participants randomized, and the number of participants in each of the categories listed below:

- ARS
  - Randomized but never dosed
- ATS
  - Completed study drug
  - o Discontinued study drug
  - o Reasons for premature discontinuation of study drug
  - Completed study
    - Rolled over into LTE
    - Did not roll over into LTE
  - Discontinued study
  - Reasons for premature discontinuation of study
- Non-e4/e4 Set
  - Completed study drug
  - Discontinued study drug
  - o Reasons for premature discontinuation of study drug
  - Completed study
    - Rolled over into LTE
    - Did not roll over into LTE
  - o Discontinued study
  - Reasons for premature discontinuation of study
- e4/e4 Set
  - Completed study drug
  - o Discontinued study drug
  - o Reasons for premature discontinuation of study drug
  - o Completed study
    - Rolled over into LTE
    - Did not roll over into LTE
  - Reasons for premature discontinuation of study

Protocol No. AL002-2 Last Revision Date: 12 Aug 2025

For the status of study drug and study completion and reasons for premature discontinuation, the number and percentage of participants in each category will be provided. The denominator for the percentage calculation for the study drug completion/discontinuation and study completion/discontinuation will be the total number of participants in the corresponding analysis set.

The following by-participant data listings will be provided by participant ID number in ascending order to support the above summary tables:

- Reasons for premature study drug or study discontinuation for the ARS,
- Reasons for screen failure for all screened participants,
- Reason why a participant is excluded from a specific analysis set (except for the Non-e4/e4 Set and e4/e4 Set) for the ARS.

